#### 7.4.3 Vital Signs

All vital signs data (body weight (kg) and systolic/diastolic blood pressure (mmHg)) will be listed by patient and visit/time. Shift tables based on notable values will be provided for vital signs. Change over time from baseline will be summarized.

Vital signs (sitting BP, HR & body weight) reporting of results will include:

- shift table baseline to worst on-treatment result
- table with descriptive statistics at baseline, one or several post-baseline time points and change from baseline to this/these post-baseline time points.

Notable Values for vital signs will include:

- Systolic blood pressure [mmHg] at baseline:  $>=180$  mmHg /  $<=90$  mmHg -
- Diastolic blood pressure [mmHg] at baseline:  $>=105$  mmHg /  $<=50$  mmHg

Notably abnormal vital signs on treatment:

- Systolic blood pressure [mmHg] on treatment:  $>=180$  mmHg with increase from baseline of  $>=20$  mmHg /  $<=90$  mmHg with decrease from baseline of  $>=20$  mmHg;
- Diastolic blood pressure [mmHg] on treatment:  $>=105$  mmHg with increase from baseline of  $>=15$  mmHg/ $<=50$  mmHg with decrease from baseline of  $>=15$  mmHg;

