#### 7.4.4 Weight on treatment: Increase $>=10\%$ / Decrease $>=5\%$ ECG

ECG data will be summarized with:

- shift table baseline to worst on-treatment result for overall assessments
- number and percentage of patients with clinically notable abnormalities will be summarized
- listing of ECG evaluations for all patients with at least one abnormality.

A "notable abnormality" is defined as:

For PR are:

---

---

Study Code: CLCI699C2X01B

- > 200 ms post-baseline and  $\leq$  200 ms at baseline
- Increase > 25% compared to baseline to a post-baseline value > 200 ms

For QRS are:

- > 110 ms post-baseline and  $\leq$  110 ms at baseline
- Increase > 25% compared to baseline to a post-baseline value > 110 ms

For QT and QTcF are:

- > 450 ms at any post-baseline and  $\leq$  450 ms at baseline
- > 480 ms at any post-baseline and  $\leq$  480 ms at baseline
- > 500 ms at any post-baseline and  $\leq$  500 ms at baseline
- an increase from baseline > 30 ms at any post-baseline
- an increase from baseline > 60 ms at any post-baseline

For HR are:

- Increase > 25% and HR > 100 bpm
- Decrease > 25% and HR < 50 bpm

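### SAP 7.4.3 labels a level-only rule for notable BP at baseline and a level-plus-change rule on treatment, so its shift table can show persistent abnormal BP as resolved

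*SAP*

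**What the plan says.** SAP 7.4.3 plans the tables in two statements. The first is "Shift tables based on notable values will be provided for vital signs". The second is a bullet, "shift table baseline to worst on-treatment result", under the lead-in "Vital signs (sitting BP, HR & body weight) reporting of results will include".

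Two sets of BP criteria follow:

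- The first set is tied to baseline ("Systolic blood pressure [mmHg] at baseline", with a matching line for diastolic) and uses level alone: SBP ≥180 or ≤90 mmHg, DBP ≥105 or ≤50 mmHg.
- The second set is headed "Notably abnormal vital signs on treatment". It uses the same levels but adds a change from baseline in the same direction: at least 20 mmHg for SBP, at least 15 mmHg for DBP.

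No level-only category is given for on-treatment values, and nothing is said about patients who are already notable at baseline.

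Weight has one criterion, which is a change: "Weight on treatment: Increase" of at least 10%, or a decrease of at least 5%. It is printed on the heading line of 7.4.4 but clearly belongs to vital signs. Heart rate has no criterion in 7.4.3. Its criteria are in 7.4.4 under ECG, and they also need a change, for example "Increase > 25% and HR > 100 bpm".

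SAP Table 5-1 names two analyses for the other secondary safety endpoint, which includes vital signs: shift tables against baseline, and proportions of patients with notable abnormalities.

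**The concern.** A shift table can be read only if the row and column categories mean the same thing. Here the row category, as labelled, is a level, and the column category is a level plus a deterioration. A patient who starts beyond the cut and stays there meets the first and fails the second, and so lands in the cell that a reader takes as improvement.

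The direction of the error matters in this trial. Under SAP 4.1.1 baseline is the end-of-treatment visit of the parent study, so a patient who is notable at baseline is already on osilodrostat. Protocol 4.5 lists both raised and lowered blood pressure among the known risks. A long-term safety table should not show persisting abnormality on drug as resolution.

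There is a second, smaller problem. The same shift table is planned for weight and heart rate, and neither has a baseline notable category, so those tables cannot be built as written.

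**Working it through.** The plan gives no figure to reproduce: protocol 12.4.2 tests no hypothesis and 12.8 has no sample size calculation. The check is to apply the two rules of SAP 7.4.3 as labelled.

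**Inputs (SAP 7.4.3).** High cut H: SBP 180, DBP 105. Low cut L: SBP 90, DBP 50. Change d: SBP 20, DBP 15 (all mmHg).

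**Rules.** Let b be the baseline value and v the worst on-treatment value.

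- Baseline notable: b ≥ H, or b ≤ L.
- On-treatment notable: v ≥ H and v − b ≥ d, or v ≤ L and b − v ≥ d.

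If b ≥ H, the patient stays notable only when v ≥ b + d. Every v from H up to just below b + d is beyond the cut but classed as not notable. On the low side the same holds for every v from L down to just above b − d.

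**Worked pairs.**

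| Measure | b | v | Change | Baseline class | On-treatment class, as labelled | Class of v by level alone |
|---|---|---|---|---|---|---|
| SBP | 182 | 182 | 0 | notable | not notable | notable |
| SBP | 182 | 195 | +13 | notable | not notable | notable |
| SBP | 182 | 202 | +20 | notable | notable | notable |
| SBP | 88 | 80 | −8 | notable | not notable | notable |
| SBP | 88 | 68 | −20 | notable | notable | notable |
| DBP | 108 | 122 | +14 | notable | not notable | notable |
| DBP | 108 | 123 | +15 | notable | notable | notable |
| DBP | 48 | 34 | −14 | notable | not notable | notable |

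**Worst values (whole mmHg) that read as not notable although still at or beyond the cut.**

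- From SBP 180: 180 to 199, because 180 + 20 = 200 is the first notable value.
- From SBP 90: 90 down to 71, because 90 − 20 = 70.
- From DBP 105: 105 to 119, because 105 + 15 = 120.
- From DBP 50: 50 down to 36, because 50 − 15 = 35.

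The band widens as the baseline becomes more extreme. From SBP 182 it runs to 201, because 182 + 20 = 202.

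**Patients not notable at baseline.** They cannot show a false improvement. Some can cross the level without being counted: SBP 170 to 185 is a rise of 15, below 20, and reads not notable at both times. That follows from using a change criterion and is defensible in a count of new abnormality. It is one more reason to keep that criterion out of a shift table.

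**Size.** The documents give no blood pressure distribution at baseline, so the number of patients cannot be derived. With the 100 patients enrolled by 8 April 2020 (protocol, Amendment 02 rationale) as denominator, each misplaced patient moves a cell by 1/100, or 1 percentage point.

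**Heart rate.** Protocol Table 8-1 and section 8.4.2 schedule only body weight and blood pressure, protocol 12.5.1.4 defines vital signs as those two, and the opening sentence of SAP 7.4.3 lists only those two. Heart rate as a vital sign therefore has no data source in the protocol.

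**The case against.** The best defence is that the SAP can be read coherently. The level-only list is the one headed as notable values, which is the term used for the shift tables. The on-treatment list has a slightly different heading. Table 5-1 names both shift tables and proportions. One could therefore use levels on both axes of the shift table and level-plus-change for the proportions. On that reading the change condition is there to capture treatment-emergent abnormality, much as the PR, QRS and QTcF criteria in 7.4.4 require a change or a baseline within the limit.

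This stands as a possibility, so a reader who infers that the SAP has committed itself to a wrong table goes too far. But the text limits the level rule to baseline and supplies only the level-plus-change rule for treatment. A programmer who follows the labels will produce the mismatch.

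It is also fair that little is lost. Nothing is tested, all values are listed by patient and visit, change from baseline is summarised, and AEs leading to discontinuation are tabulated. The special-interest list in SAP 8.1 includes terms for raised blood pressure. It has none for low blood pressure, but such events would still appear in the general AE tables if reported.

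Three stronger inferences are tempting, and the documents do not support them:

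- *That a large share of patients would be misclassified.* Any such percentage would rest wholly on assumed blood pressure distributions.
- *That the proportion with notable abnormalities is missing from the plan.* Table 5-1 names it. What 7.4.3 lacks is an explicit line like the ECG one in 7.4.4, "number and percentage of patients with clinically notable abnormalities will be summarized".
- *That a heart-rate shift table could be rescued from data already collected as vital signs.* The protocol collects no vital-sign heart rate.

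**Conclusion.** The concern holds as a fault in a descriptive safety table. Followed as labelled, SAP 7.4.3 shows a patient who is notable at baseline, and whose blood pressure is unchanged or worse by less than 20 mmHg (SBP) or 15 mmHg (DBP), as going from notable to not notable. Larger worsening is still shown as notable.

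The classification result is exact and needs no distributional assumption. It rests on one reading: that the labels for baseline and for treatment decide which rule goes on which axis. How many patients fall in the affected cells is unknown and may be none.

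The primary AE analysis is not touched and no data are lost. The wording should still be corrected before the final tables are produced, because the error runs towards reassurance on a known risk. The SAP already has the right pattern: for laboratory tests without CTCAE grades, 7.4.2 uses a single low/normal/high scale for both baseline and worst value.

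**What to change.** Revise SAP 7.4.3 and the table shells as follows.

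1. **Blood pressure shift table.** Use the same level-only categories on both axes: SBP ≥180, >90 to <180, ≤90 mmHg; DBP ≥105, >50 to <105, ≤50 mmHg. Tabulate the worst high and the worst low value separately. Protocol 8.4.2 takes three readings; categories with open boundaries leave no gap if these are averaged (a mean of 179.33 still falls in the middle category).
2. **Level-plus-change rule.** Keep it, and state in 7.4.3 that it defines the proportion with notable abnormalities already named in Table 5-1.
3. **Weight.** Report increases of at least 10% and decreases of at least 5% as counts and percentages, not as a shift, because weight has no baseline notable category.
4. **Heart rate.** Remove it from the vital-sign shift table and leave it under ECG in 7.4.4.

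The cost is SAP wording, table shells and slightly longer safety output. No new data are needed, and the interim outputs listed in SAP 2.3 include no vital-sign table. These are reporting categories only and imply nothing about clinical management.

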#### 7.4.4 Weight on treatment: Increase $>=10\%$ / Decrease $>=5\%$ ECG

ECG data will be summarized with:

- shift table baseline to worst on-treatment result for overall assessments
- number and percentage of patients with clinically notable abnormalities will be summarized
- listing of ECG evaluations for all patients with at least one abnormality.

A "notable abnormality" is defined as:

For PR are:

---

---

Study Code: CLCI699C2X01B

- > 200 ms post-baseline and  $\leq$  200 ms at baseline
- Increase > 25% compared to baseline to a post-baseline value > 200 ms

For QRS are:

- > 110 ms post-baseline and  $\leq$  110 ms at baseline
- Increase > 25% compared to baseline to a post-baseline value > 110 ms

For QT and QTcF are:

- > 450 ms at any post-baseline and  $\leq$  450 ms at baseline
- > 480 ms at any post-baseline and  $\leq$  480 ms at baseline
- > 500 ms at any post-baseline and  $\leq$  500 ms at baseline
- an increase from baseline > 30 ms at any post-baseline
- an increase from baseline > 60 ms at any post-baseline

For HR are:

- Increase > 25% and HR > 100 bpm
- Decrease > 25% and HR < 50 bpm

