- Changes in body weight and blood pressure: potentially increased by mineralocorticoid effect of the aldosterone precursor 11-deoxycorticosterone
- Changes in sex hormones: testosterone and estradiol increased (testosterone more than estradiol)

In addition, treatment with osilodrostat can potentially result in neutropenia, which is considered to be an indirect effect of cortisol reduction, as reported in the literature. During hormonal control, a significant decrease of neutrophil count, which is commonly elevated in patients with CD, has been reported demonstrating the effect of glucocorticoids on these blood cells ([Masri-Iraqi et al 2014](#)). This effect has also been observed with osilodrostat in the CD trials and has included cases of neutropenia which were associated with cortisol levels that were either below normal or have had a rapid and substantial decline from baseline. In the cases observed to date, neutropenia has rapidly reversed with discontinuation of osilodrostat, and has also reversed when osilodrostat was continued, typically with decreasing doses.

For a comprehensive review of clinical safety data with osilodrostat, see the [\[Investigator's Brochure\]](#).

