In this study, 12 CD patients received osilodrostat orally for 10 weeks. The drug was given at the starting dose of 2 mg b.i.d., and was progressively increased on the basis of the urinary

cortisol levels till their normalization or a maximum dose of 50 mg b.i.d. was achieved. After 10 weeks of treatment, all 12 patients normalized urinary cortisol levels or achieved a > 50% reduction in urinary cortisol levels. The reduction of urinary cortisol levels was accompanied by a trend towards a decrease in BP. Osilodrostat was generally well tolerated, with the most frequently reported adverse events being fatigue (58.3%), nausea (41.7%), diarrhea (25%), headache (25%), hypokalemia (25%), muscle spasms (25%) and vomiting (25%).

Recently, an amended extension of the phase II study (CLCI699C2201, LINC 2) is currently ongoing with the overall objective of evaluating the efficacy and safety of osilodrostat for a longer period of time. After 22 weeks of treatment, 15 out of 19 patients (78.9%) had normalized UFC. The decrease in urinary cortisol levels was associated with improvements in the glucose and lipid profiles. Adverse events during this extension of the study included GI disturbances (nausea and diarrhea in 31.6%), asthenia (31.6%) and adrenal insufficiency (31.6%), together with an increase in ACTH, cortisol and aldosterone precursors, and an increase in testosterone, which, in some women was associated with onset or worsening of acne and hirsutism.

There was a trend toward improved fasting glucose and HbA1c in patients with diabetes at baseline, and an improved fasting lipid profile in patients with dyslipidemia at baseline.

After the initial 22 weeks (core study), patients were invited to enter the extension study up to month 31. Safety and efficacy results have shown that the drug's profile will fulfill the unmet need in the medical management of endogenous hypercortisolism because:

- Normal UFC was maintained for >2.5 years in a majority of patients.
- None of the patients with normalization of cortisol experienced escape from response
- Clinical measures improved, particularly body weight and BMI
- Occurrences of the most commonly reported AEs decreased over time

Therefore, osilodrostat seems to be a promising drug for the treatment of CD, with a satisfactory safety and tolerability profile.

Risks of osilodrostat treatment in study population

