Known risks of treatment with LCI699 in patients with CS include: QT prolongation, hypocortisolism/adrenal insufficiency, AEs related to the accumulation of precursor molecules, including: increased or decreased blood pressure, hypokalemia or hyperkalemia, hyponatremia, weight gain, edema, and increase in the synthesis of sex steroids (primarily adrenal androgens in women) that may lead to menstrual changes and hirsutism in women and acne in either men or women. Skin rash has been observed. Corticotroph tumor progression, with or without compressive symptoms, is a potential risk.

Neutropenia has been observed in a small number of patients with CD receiving osilodrostat. Preliminary assessment suggests that these events might be associated with cortisol levels that are either below normal or have had a rapid and substantial decline from baseline. In the observed cases, neutropenia rapidly reverses either spontaneously (typically after dose decrease) or with discontinuation of osilodrostat.

In addition, the protocol provides specific guidance for safety follow-up for liver toxicity (increased transaminases, increased total bilirubin) and an algorithm for monitoring and management of QT prolongation.

Conclusion

The treatment of patients with CS still represents a challenge: the available treatments do not lead to biochemical control in quite a large number of patients and many of them lose biochemical control over time.

Therefore there is an unmet medical need to develop new drugs with improved safety, efficacy and a more patient-friendly profile.

Based on current safety and efficacy data of osilodrostat, the overall benefit-risk of trial participation is expected to be positive for all subjects to be enrolled in this study.

5 Population

The investigator or designee must ensure that only patients who meet all the following inclusion and none of the exclusion criteria are offered treatment in the study.

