Symptomatic hypocortisolism or adrenal insufficiency	If the investigator at any time suspects hypocortisolism or adrenal insufficiency, they can immediately interrupt study drug and initiate replacement with glucocorticoids. Upon recovery as assessed by the investigator, glucocorticoid therapy can be tapered as tolerated, and study drug can be re-started. The decision to restart study drug will be made by the investigator. The AE and associated treatments with changes to study drug need to be appropriately documented in the eCRF. Recovery is assessed clinically by the investigator. A general guideline is that glucocorticoid taper can begin when cortisol in the upper part of the normal range or > ULN*, and study drug can be re-started if the patient is clinically stable off glucocorticoid therapy for at least one week, and the cortisol is normal or > ULN.
Persistent asymptomatic hypocortisolism (cortisol < LLN) at the lowest dose of LCI699 (1 mg every other day)	The investigator can interrupt study drug and restart at the same dose as clinically indicated.
Glucocorticoid withdrawal syndrome	Reduce or withhold dose until improved
*Hypotension (mild, reversible)	Reduce or withhold dose until improved
*Hypertension	Reduce or withhold dose until improved; consider angiotensin-converting-enzyme (ACE) inhibitors if appropriate for treatment of hypertension, or spironolactone as a second line treatment, particularly if hypokalemia is present. ACE inhibitors and spironolactone should not be used in combination.
*Weight gain, edema	Reduce or withhold dose until improved; consider spironolactone for treatment of edema.
*Hypokalemia	Consider reducing or withholding dose until improved; replace potassium; consider spironolactone or eplerenone for prevention and treatment of hypokalemia
*Hyperkalemia	Consider reducing or withholding dose until improved; if on spironolactone or eplerenone, reduce or withhold; treat with kayexalate and other potassium lowering therapies as needed.

Toxicity	Suggested Actions
*Hirsutism (women only)	Reduce or withhold dose until improved; review testosterone level; consider spironolactone, cyproterone acetate or finasteride per local guidelines.
*Acne (women or men)	Reduce or withhold dose until improved; review testosterone level; consider spironolactone, cyproterone acetate or finasteride per local guidelines.

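### SAP 7.4.3 flags weight gain only at >=10% but weight loss at >=5%, gives no reason, and so is less sensitive in the direction the protocol names as a drug risk

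*SAP*

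**What the plan says.** SAP 7.4.3 (Vital Signs) ends its list of on-treatment notable values with the weight criterion "Weight on treatment: Increase $>=10\%$ / Decrease $>=5" (percent), displaced into the heading of 7.4.4. No rationale follows. The same section promises a "shift table baseline to worst on-treatment result", says that the vital-sign shift tables rest on notable values, and gives descriptive statistics of change from baseline at one or more time points. It also states: "All vital signs data (body weight (kg) and systolic/diastolic blood pressure (mmHg)) will be listed by patient and visit/time". SAP Table 5-1 makes shift tables and proportions of patients with notable abnormalities the planned analysis for this group of secondary safety measures.

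On the direction of risk, Protocol 1.2.1.2.2 lists "Changes in body weight and blood pressure: potentially increased by mineralocorticoid effect of the aldosterone precursor 11-deoxycorticosterone". Protocol 4.5 includes "hypokalemia or hyperkalemia, hyponatremia, weight gain, edema" among the known risks, and Table 6-2 has a row for "Weight gain, edema". On benefit, Protocol 4.5 reports from the phase II extension: "Clinical measures improved, particularly body weight and BMI".

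**The concern.** The gain limit is twice the loss limit, and gain is the direction the protocol associates with precursor accumulation. In a single-arm study no comparator shows how often each flag would be raised without a drug effect, so a reader will tend to set the notable-gain row against the notable-loss row. With unequal limits, that comparison mostly reflects the limits.

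Also at stake is a group of patients, those whose largest gain is 5 to <10%, that no planned table counts by size of gain. The special-interest list in SAP 8.1 does not fill the gap: its precursor-accumulation group holds oedema, hypertension and hypokalaemia terms, but no group holds a weight term.

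**Working it through.** **Inputs from the documents.** Limits: +10% and −5% (SAP 7.4.3). Baseline: End of Treatment in the parent study (SAP 4.1.1). Visits: every 12 weeks (Protocol 3.1). The plan gives no expected count to reproduce; Protocol 12.8 marks sample size as not applicable and no hypothesis is tested.

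**Not in the documents, so assumed.** Variability of weight within a patient, and the number of visits per patient.

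**Step 1: scale.** For an 80 kg patient the flags need a gain of 0.10 × 80 = 8 kg or a loss of 0.05 × 80 = 4 kg.

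**Step 2: one visit, in closed form.** Let percent change be normal with mean m and SD s. Then P(gain flag) = 1 − Φ((10 − m)/s), P(loss flag) = Φ((−5 − m)/s), and P(gain of 5 to <10%) = Φ((10 − m)/s) − Φ((5 − m)/s). For m = 0, s = 6: 1 − Φ(1.667) = 4.8%, Φ(−0.833) = 20.2%, and 15.5% between. Per 100 patients:

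| m | s | gain >=10% | loss >=5% | gain 5 to <10% |
|---|---|---|---|---|
| 0 | 4 | 0.6 | 10.6 | 9.9 |
| 0 | 6 | 4.8 | 20.2 | 15.5 |
| 0 | 8 | 10.6 | 26.6 | 16.0 |
| 0 | 10 | 15.9 | 30.9 | 15.0 |
| +2 | 4 | 2.3 | 4.0 | 20.4 |
| +2 | 10 | 21.2 | 24.2 | 17.0 |

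With no true change, flagged losses outnumber flagged gains 17-fold (s = 4) down to 1.9-fold (s = 10). With a true mean gain of 2%, losses still lead slightly.

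**Step 3: any visit, no mean change, by simulation.** There were 400,000 patients per setting. Change is exp(z_t − z_0) − 1, where z is log weight. In the AR(1) model, z is stationary with the SD shown and correlation 0.7 between successive visits. In the random walk, z has the annual SD shown, with 1% noise at baseline and at each visit. Entries are the percentage of patients with any loss >=5% v any gain >=10%.

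| Model | 4 visits | 12 visits | 20 visits |
|---|---|---|---|
| AR(1), SD 3% | 13.3 v 0.7 | 33.2 v 4.5 | 43.6 v 7.7 |
| AR(1), SD 4% | 24.6 v 4.0 | 48.2 v 15.2 | 59.1 v 22.5 |
| AR(1), SD 5% | 33.5 v 9.6 | 57.8 v 27.0 | 68.0 v 36.8 |
| Random walk, 2%/yr | 2.5 v 0.0 | 15.6 v 0.7 | 26.5 v 3.4 |
| Random walk, 3%/yr | 8.1 v 0.2 | 29.1 v 5.6 | 41.0 v 13.4 |
| Random walk, 4%/yr | 15.1 v 1.2 | 39.2 v 13.2 | 50.5 v 24.0 |
| Random walk, 5%/yr | 21.8 v 3.6 | 46.5 v 21.0 | 57.0 v 32.9 |

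At 20 visits the ratio runs from 57.0/32.9 = 1.7 to 26.5/3.4 = 7.8. With 5% in both directions the two rates differ by at most 2.9 points (43.6 v 46.5, AR(1) SD 3%, 20 visits).

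**Step 4: sustained gain.** A shift of 0.04 in log weight is exp(0.04) − 1 = 4.1%. AR(1), 12 visits:

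| SD | any gain >=5% | any gain >=10% | peak gain 5 to <10% | any loss >=5% |
|---|---|---|---|---|
| 3% | 82.5 | 29.0 | 53.5 | 5.7 |
| 4% | 84.4 | 44.6 | 39.8 | 17.3 |
| 5% | 85.5 | 54.9 | 30.6 | 29.5 |

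Between 31% and 54% of patients peak at 5 to <10% and are not flagged for gain, but flagged gains exceed flagged losses at each SD.

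**The case against.** Three stronger readings are tempting, and the documents support none of them.

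- **That gains of 5–10% are never counted.** They are missing only from notable-value and shift output. Every weight is listed by patient and visit. The change-from-baseline summaries include minimum and maximum (SAP 4.1), so the largest gain at each summarised visit is visible. A gain reported as an adverse event enters the AE tables, which are the primary endpoint.
- **That the output is skewed toward the expected benefit.** A flagged loss appears under notably abnormal vital signs, as an abnormality. Loss is not purely benefit here: the protocol lists nausea, vomiting and diarrhoea as common events. The reported weight improvement comes from an earlier study, whereas baseline here is the end of parent-study treatment, so further loss is not shown to be expected.
- **That a real shift toward gain would mostly be missed.** This depends on the assumed SD. Under the 4% gain over 12 visits, 29% reach +10% at SD 3% but 55% at SD 5%, and the table points the right way.

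The size is also open to challenge. Twenty visits is close to the maximum: five years from first patient first visit gives 5 × 52/12 ≈ 21.7 visits, enrolment was staggered (23 patients by January 2019, 100 by April 2020), and patients leave when the drug becomes commercially available. The correlation of 0.7 has no source; at 0.9 over 12 visits the AR(1) loss rates fall to 15–39%. Blood pressure is a weak precedent: its change components match (20/20 and 15/15 mmHg), but each also needs an absolute limit, and no principle of symmetry is stated.

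What stands is that the limits are unequal, unexplained and wider on the side of the named risk, and no planned table counts patients with a gain of 5 to <10%.

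**Conclusion.** The point holds in a limited form. Gain is flagged less sensitively than loss, the two counts are not comparable, and gains of 5 to <10% enter no notable-value count. With no mean change, in the models assumed, any loss >=5% against any gain >=10% is about 3–34% v 0–10% of patients over 4 visits, 16–58% v 1–27% over 12, and 27–68% v 3–37% over 20. The direction follows from the limits whenever changes are roughly symmetric about zero; the size rests on assumed variability and follow-up.

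No passage contradicts the limits, no decision rule uses them, and the study is descriptive. This is therefore a cheap improvement to reporting rather than an error in the plan.

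**What to change.** In SAP 7.4.3, replace the single weight line with the number and percentage of patients with an increase >=5% and >=10%, and with a decrease >=5% and >=10%. Show each at any on-treatment visit and at the last on-treatment visit; the any-visit figure grows with follow-up and needs a fixed-point companion. Both existing rows are kept, and graded bands already have a precedent in the SAP's QTcF criteria (450/480/500 ms; 30/60 ms). If the unequal limits are deliberate, state why.

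In the same edit, move the line out of the ECG heading, and state which weight categories apply at baseline and which direction counts as worst; the weight shift table now lacks both.

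The cost is a short SAP edit and a few table rows from data already in the eCRF. The downside is a higher reported percentage of patients with weight gain.

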1.2.1.2.3 Osilodrostat: QT/QTc in healthy volunteers

The potential impact of osilodrostat on cardiac repolarization potential was assessed in the definitive ICH E14 compliant thorough QT Study (TQT) study LCI699C2105 in 86 healthy male and female subjects.

Based on the predicted exposure levels, the predicted maximum mean QTcF on osilodrostat 30 mg is 6.3 ms (CI 5.13, 7.42).

The results remained below the QTcF effect of regulatory concern (i.e., an upper boundary of the 90% CI < 10 ms) and fully support the use of LCI699 doses up to 30 mg b.i.d.

2 Objectives and endpoints

Objectives and related endpoints are described in [Table 2-1](#) below.

Table 2-1 Objectives and related endpoints

Objective(s)	Endpoint(s)
Primary Objective(s) 
• To evaluate long term safety data	Endpoint(s) for primary objective(s) 
• Frequency and severity of AEs/SAEs;
Secondary Objective(s) 
• To evaluate clinical benefit as assessed	Endpoint(s) for secondary objective(s) 
• Proportion of patients with clinical benefit as assessed by the Investigator at scheduled visits

Objective(s)	Endpoint(s)
by the investigator. • To evaluate long term safety data	• Frequency, severity and summaries of relevant safety assessments. Safety assessments include: laboratory evaluations, vital signs (blood pressure and body weight), ECG and pituitary MRI.

3 Study design

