### 5 VARIABLES AND ENDPOINTS

Objectives and related endpoints are described in [Table 5-1](#) below altogether with the planned analysis of collected data.

Study Code: CLCI699C2X01B

Table 5-1 Objectives and related endpoints

Objective	Endpoint	Analysis
Primary		
To evaluate long term safety data, i.e., SAEs and AEs	Frequency and severity of AEs/SAEs	The assessment of safety will be based on the frequency and severity of adverse events (AEs) and serious adverse events (SAEs)
Secondary		
To evaluate clinical benefit as assessed by the investigator	Proportion of patients with clinical benefit as assessed by the investigator at scheduled visits	Proportion of patients with clinical benefit as assessed by the investigator will be summarized at scheduled visits
Other secondary		
To evaluate other safety data and tumor size	Lab parameters, vital signs, ECG, Tumor size and longest dimension	Shift tables vs Baseline and proportions of patients with notable abnormalities or grade 3 or 4

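### QTcF is summarised only in categories, so the planned outputs do not show average QTcF drift since roll-over, and the any-visit percentages grow with the number of ECGs

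*SAP*

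**What the plan says.** SAP 7.4.4 (ECG) lists three outputs:

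- A shift table of the overall ECG assessment, from baseline to the worst result on treatment.
- A count, given in these terms: "number and percentage of patients with clinically notable abnormalities will be summarized".
- For individual data, not every patient but only a "listing of ECG evaluations for all patients with at least one abnormality".

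For QT and QTcF, a notable abnormality is a new value above 450, 480 or 500 ms, or one of two change criteria. The lower one is "an increase from baseline > 30 ms at any post-baseline"; the upper one has the same form with 60 ms in place of 30 ms.

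SAP Table 5-1 gives one analysis for laboratory values, vital signs, ECG and tumor size: "Shift tables vs Baseline and proportions of patients with notable abnormalities or grade 3 or 4".

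Two of those domains get more elsewhere in the SAP. For vital signs, 7.4.3 adds a "table with descriptive statistics at baseline, one or several post-baseline time points and change from baseline". For tumor volume, 7.4.5 adds actual values and change from baseline by visit. ECG intervals get no such addition.

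Protocol 4.5 names QT prolongation first among the known risks. Protocol Table 2-1 and section 12.5 place ECG in the secondary safety objective. Protocol 8.4.4 has the ECGs read on site and recorded in the eCRF.

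**The concern.** QTcF is a continuous measurement, taken repeatedly over years of treatment. A modest upward drift across the whole group moves few patients over a cut-off at any one ECG, so categorical outputs are a blunt way to see it. The listing covers only patients with an abnormality, so a reader of the study report could not rebuild the average either.

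The any-visit form adds a second difficulty. Each further ECG is another chance for ordinary variation to cross +30 ms. A patient followed for four years is more likely to be counted than one followed for one year, even if QTcF has not changed in either. The worst-value shift table has the same property. Nothing planned separates length of follow-up from real change, so a sizeable percentage could be read as a signal and a real drift could be put down to noise.

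**Working it through.** **1. Is a continuous QTcF summary planned anywhere?**

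- SAP 7.4.4 and Table 5-1: categories and a restricted listing only.
- SAP 4.1: sets the layout of tables of continuous variables, but does not create a QTcF table.
- SAP 2.3 (interim outputs): tables and listings of QT-prolongation and arrhythmia adverse events, with no ECG measurements.
- Protocol 12.5.1.4: covers vital signs and pituitary MRI, with no ECG analysis.

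None is planned. The plan states no sample size, power or SD for QTcF, so there is no figure of its own to reproduce.

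**2. Inputs**

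- n = 100: enrolled at 8 April 2020 (Protocol, Amendment 02 rationale). The final number is not given.
- ECGs per patient: Protocol Table 8-1 marks four after baseline (week 24, week 48, end of treatment, follow-up). Protocol 4.5 says every 24 weeks, and the study is open for about 5 years: 5 × 365.25 / 7 / 24 = 10.9, so at most about 10. I show one to eight.
- SD of a patient's QTcF change, σ: not in the documents. Assumed 15 to 25 ms.
- Correlation of 0.5 between a patient's changes: assumed. It is what a shared baseline measurement gives when all ECGs have equal error.
- A drift of 6.3 ms, used only as a scale.

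**3. Effect of the number of ECGs**

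With normal changes, mean drift μ and k ECGs:

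P(any change > 30) = 1 − ∫ φ(u) · Φ((30 − μ)/(σ/√2) − u)^k du

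For k = 1 this is 1 − Φ((30 − μ)/σ). For example, at σ = 20 and μ = 0 it is 1 − Φ(1.5) = 6.7%.

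| ECGs | SD 15, no drift | SD 15, drift 6.3 ms | SD 20, no drift | SD 20, drift 6.3 ms |
|---|---|---|---|---|
| 1 | 2.3% | 5.7% | 6.7% | 11.8% |
| 2 | 4.1% | 9.9% | 11.5% | 19.5% |
| 4 | 7.2% | 16.2% | 18.5% | 29.6% |
| 8 | 11.6% | 24.3% | 27.3% | 41.1% |

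At SD 20, a second ECG with no drift (11.5%) gives almost the same percentage as one ECG with a 6.3 ms drift (11.8%). The percentage alone cannot tell the two apart.

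**4. Precision of the missing summary**

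The 90% CI half-width for a mean change is t(0.95, n − 1) × σ/√n. At n = 100, t = 1.660:

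- SD 15: 1.660 × 15/10 = 2.5 ms
- SD 20: 1.660 × 20/10 = 3.3 ms
- SD 25: 1.660 × 25/10 = 4.2 ms

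At n = 50 (t = 1.677), which stands for a later visit after attrition, the half-widths are 3.6, 4.7 and 5.9 ms.

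**The case against.** **Cut-offs are the right scale for this study.** Protocol 6.5.1.2, 8.4.4 and 9.1.1 manage patients by cut-offs at 480 ms, 500 ms and +60 ms. SAP 7.4.4 counts exactly these, and QT-prolongation and arrhythmia events are also summarised as adverse events of special interest. This stands, and it is why the counts should stay. It does not supply an average.

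**ECG is not singled out.** SAP 7.4.2 also summarises laboratory data only in categories. This stands: a reader who compares ECG with vital signs alone might infer that it is the sole exception, and it is not.

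**The thorough-QT benchmark does not transfer.** Protocol 1.2.1.2.3 reports a predicted maximum mean effect of 6.3 ms against a 10 ms bound, from 86 healthy volunteers. A reader might infer that a mean change in this study could be set against those figures. It could not. By SAP 4.1.1, baseline is the parent study's End of Treatment visit, patients roll over at their last dose, and there is no control arm. The change is on drug minus on drug.

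**The loss of information is smaller than it first looks.** At one ECG, with n = 100 and a 6.3 ms drift, power for the mean change is 99%, 88% and 70% (SD 15, 20, 25), against 35%, 40% and 35% for the +30 ms count. That is a gap of 35 to 64 points. The planned count is any-visit, however. At eight ECGs the gap is about 9 points at SD 15 (1.00 against 0.912) and 17 at SD 20 (0.986 against 0.821). Both comparisons treat the no-drift rate as known, which favours the count. The study also tests no hypothesis, so power only measures information here and the single-ECG gap should not be the headline.

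**The added table has weaknesses.** ECGs are read locally on site equipment. Patients stopped for QT prolongation leave the later visits, so by-visit means lose those most affected. Both points stand and call for showing N and adding a last on-treatment row.

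**Conclusion.** The gap is real and worth closing, as a should-fix item. The planned outputs do not show average QTcF drift since roll-over. The any-visit percentages mix real change with the number of ECGs: with no true change, the share above +30 ms rises from 2-7% at one ECG to 7-18% at four and 12-27% at eight. These percentages rest on an assumed SD of 15 to 20 ms, normal changes and a correlation of 0.5. The precision figures rest on n = 100 and an assumed SD of 15 to 25 ms.

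A reader might go further and conclude that the study cannot show a QTcF shift. The documents do not support that: the ECGs are in the eCRF and the baseline values are in the EG transfer (SAP 5.3 and attachment 8.2). The omission is in the planned outputs, not in the data.

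**What to change.** In SAP 7.4.4 and Table 5-1:

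- Keep all the cut-off counts.
- Add a table of QTcF, PR and QRS with N, mean, SD, median, minimum and maximum at baseline and each scheduled ECG visit, with change from baseline and a 90% CI for the mean QTcF change. Heart rate is already covered by the vital-signs table in 7.4.3.
- Add change from baseline to the last on-treatment ECG, which does not depend on staying in the study to a given visit.
- Print the number of post-baseline ECGs per patient beside the any-visit rows.
- Footnote that baseline is the parent study's End of Treatment visit on drug with no control, so the change is drift since roll-over and is not comparable with the thorough-QT 6.3 ms or 10 ms figures.

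The cost is SAP wording and one or two extra tables, with no new assessments. The downside is noisy, locally read values and a by-visit N that falls selectively, so later visits need to be read with care.
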